4.4.2 Secondary Efficacy Endpoints

4.4.2.1 Time to Event Endpoints

Time to event endpoints include the following: TTR of all symptoms, TTR of individual symptoms, time to cessation of viral shedding and time to resolution of fever. These endpoints will be summarized using Kaplan-Meier tables and graphs. Viral shedding will be studied also per virus strain. The median TTR and associated 95% CIs will be estimated for each of the two treatment groups. The exact CIs of the median differences of Hodges-Lehmann (HL) estimators will be derived using the PROC NPAR1WAY in SAS. The protocol mentioned bootstrapping, however in SAS, bootstrapping calculates differences between medians, when the correct estimator in skewed distributions is the median of differences (or HL estimator). Asymptotic theory exists to obtain those CI (aka Moses CI).

Patients who have not experienced the event, e.g. resolution of all symptoms, by the last day of contact will be censored at this time. Patients who withdraw from the study without experiencing the event will be censored at the time of withdrawal (see [Appendix 7](#)).

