4.9 MISSING DATA

As no formal statistical analyses will be carried out, imputation methods for missing data for the purposes of statistical model fitting are not required.

For the derivation of time to resolution of symptoms endpoints, a missing symptom score will be estimated by linear interpolation between the previously available assessment and the subsequent available assessment. (More details are provided in [Appendix 7](#)).

For the derivation of time to resolution of fever, a missing temperature entry will be estimated by linear interpolation between the previously available assessment and the subsequent available assessment.

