Per 2016 FDA feedback: *'the previously-listed substitutions A28T and R124M are now referred to as A11T and R453M, respectively, consistent with the convention of numbering from the beginning of the processed HA (without the signal peptide). We removed previously listed substitutions that were identified in strains not currently relevant to humans (H154Q in H1N9).'*" In summary, per FDA communication the HA residues to be included on the resistance list (renamed nomenclature, taking into account only the mature protein, w/o the signal peptide) are A11T, K173G, and R453M in H3N2; and H99Q in influenza B virus (no HA mutations listed for H1N1)

12. **APPENDIX 7: ALGORITHMS USED FOR DERIVATION AND SUMMARIES OF TIME TO ALLEVIATION OF ALL SYMPTOMS**

[figure not shown]
The purpose of this document is to describe the algorithm used to derive and analyse the Time To Resolution of all symptoms in the Tamiflu program (adults + adolescents).

Time to alleviation (TTA) of all symptoms (Efficacy VAD variable TALLSYMP), was calculated as the time **from start of study drug (Time=0) to the start of the first 24 hour period in which** all 7 symptoms were less than or equal to 1 and they remained at one or less for at least 21.5 hours, i.e., up to the end of the 21.5 hour period.

Example of Calculation of the Primary Efficacy Parameter: Time to Alleviation of all Symptoms

Pharmaceuticals

For subjects with missing data or who withdrew or ceased recording data prior to alleviation, data was imputed according to the following rules:

At the individual symptom level, a missing value was estimated by linear interpolation between the previously available assessment and the subsequently available assessment.

If the interpolated value was ≤ 1 for the first time (e.g. interpolation between a score of 2 and 0 gave 1) then the interpolated time point was not considered as the beginning of the 24 hour period that determined whether alleviation of that symptom had occurred, instead, the beginning of the 24 hour period started at the next observed time point at which the value was ≤ 1 . The VAD variables which denote missing data rules are TESTTYPE AND DATETYPE (refer to the efficacy VAD specifications for details).

If symptoms were missing, 0 or 1 at baseline and were subsequently recorded as missing, 0 or 1 for at least 21.5 hours, then the TTA of all symptoms was set to

missing. [Corresponding Efficacy VAD variables TALLSYMP=. And CENSORED=0.]

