If all non-missing baselines symptoms were > 1 at baseline and recovered (<=1) immediately and remained <=1 for at least 21.5 hours OR if all non-missing baselines symptoms were > 1 at baseline and no further recordings of symptom scores had been recorded, then the Time to Alleviation of All symptoms was 0.

[Corresponding Efficacy VAD variables TALLSYMP=0 and CENSORED=0]

For Paediatric studies, should a subject only have No/mild symptoms from baseline onwards, and subsequent visits satisfy the 21.5 hour rule, then set TALLSYMP=0 and CENSORED=0.

Subjects withdrawing prior to alleviation of symptoms were **censored** at the time of withdrawal. [denoted in the efficacy VAD as CENSORED=1]

The primary endpoint was compared between groups using statistical methodology appropriate for survival data since censored data is present. The within-treatment group summary measures of median duration, was estimated from the Kaplan-Meier curve. A weighted Mantel-Haenszel test was used to formally test for a between-treatment group effect since the proportional hazards assumption was considered unlikely to hold *a priori*.

The weighting scheme used was the generalised Gehan Wilcoxon weights in which the weighting is equal to the number in the risk set.

Kaplan-Meier graphs of duration of symptoms according to treatment group were provided. Estimates of the difference between median durations were provided by subtracting the observed treatment group medians obtained from the Kaplan-Meier curve and estimating between group variability through bootstrapping. The dataset was sampled 2000 times in order to provide 95% confidence intervals using the percentile method (Efron 1993).

The bootstrap methodology had previously been applied within the influenza clinical trial field by the MIST group (MIST 1998) when comparing time to alleviation of illness in subjects treated with inhaled Zanamivir or placebo.

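### Three zero-time rules for symptom and fever resolution conflict with the SAP's own event, missing-value and fever definitions

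*SAP*

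**What the plan says.** **(a) No diary after baseline.** Appendix 7 opens its rules with "For subjects with missing data or who withdrew or ceased recording data prior to alleviation, data was imputed according to the following rules". One of them says that if every non-missing baseline symptom was above 1 and "no further recordings of symptom scores had been recorded, then the Time to Alleviation of All symptoms was 0"; the attached coding is TALLSYMP=0 with CENSORED=0, an event at time zero. The same appendix defines alleviation as all seven symptoms at 1 or below for at least 21.5 hours, and says "Subjects withdrawing prior to alleviation of symptoms were" censored at withdrawal. Section 2.2.2.1 allows a zero from a baseline above 1 only when scores of 1 or less follow at once and last 21.5 hours. Section 4.4.2.1 says patients without the event "by the last day of contact will be censored at this time", and "Patients who withdraw from the study without experiencing the event will be censored at the time of withdrawal"; it refers to Appendix 7 at that point. Section 4.9 also refers to Appendix 7 for missing scores.

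**(b) Children never above 1.** For all-symptom resolution in children, Section 2.2.2.1 sets a child at 1 or below at baseline who stays there to missing. Its next sentence sets what reads as the same child to zero. Appendix 7 sets such a subject in paediatric studies to zero, uncensored.

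**(c) Fever.** Section 2.2.2.1 defines time to resolution of fever by the last reading at or above 37.8°C. It then gives zero to a patient febrile at baseline whose first post-baseline reading is below 37.8°C, without requiring that fever stay away.

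**The concern.** Under (a), a patient with only moderate or severe scores on record, and no observed improvement, counts as recovered at once. The rule is also uneven: a no-diary patient with one mild baseline symptom falls outside it, while one with every symptom moderate or severe falls inside.

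The scope is unclear as well. Appendix 7 is in the past tense and describes "the algorithm used to derive and analyse the Time To Resolution of all symptoms in the Tamiflu program (adults + adolescents"). It may govern NV20234, the historical data, or both. If only one side carries the zeros, the two sides of the historical placebo comparison use different event rules. False zeros only in NV20234 would favour oseltamivir; false zeros only in historical placebo would count against it. Use on both sides would partly cancel.

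The zero also reaches the Hodges-Lehmann difference, whose interval is to be "derived using the PROC NPAR1WAY in SAS". An ordinary Hodges-Lehmann estimate uses the time value alone, so changing only the censoring flag would leave the zero in place.

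Under (b), event status in the under-13 tables depends on which sentence the programmer follows. Under (c), a patient whose fever returns can be given a time of zero.

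**Working it through.** The SAP gives no count of affected patients and no expected median, so there is no plan figure on this point to reproduce. First apply the competing rules to the same patient.

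| Patient | One rule | Competing rule |
|---|---|---|
| (a) All baseline scores >1, no later diary | Appendix 7: event at 0 | 4.4.2.1 and Appendix 7: censored |
| (b) Child ≤1 at baseline, stays ≤1 | 2.2.2.1, first sentence: missing | 2.2.2.1, next sentence: zero; Appendix 7: event at 0 |
| (c) Febrile baseline, afebrile first reading, fever returns | 2.2.2.1 zero rule: 0 | 2.2.2.1 definition: time of last febrile reading |

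For (a), interpolation does not help. Section 4.9 says "a missing symptom score will be estimated by linear interpolation between the previously available assessment" and the next one, and here there is no next one.

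For (c), take invented readings of 38.5 (0 h), 37.5 (12 h), 38.4 (24 h) and 38.1 (36 h), then afebrile. The definition gives 36 h; the zero rule gives 0. If fever had not returned, the last febrile reading would be baseline and both would give zero.

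**Illustrative size of (a).** Inputs: 75 per arm and a relevant difference of 34 h with SD 98 h (Section 2.3). Assumptions: exponential times with true median M, k affected patients, no other censoring, f = k/75. M is taken as 68 h (an exponential with SD 98 h has median 98 × ln 2 = 67.9 h) or 120 h.

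- Events at 0: (1 − f)·S(m) = 0.5, so m = M·[1 + log2(1 − f)].
- Censored at 0: m = M.
- Censored at a late last contact: f + (1 − f)·S(m) = 0.5, so m = −M·log2[(0.5 − f)/(1 − f)].

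For k = 2 and M = 120 h, f = 0.02667:
- Events at 0: 120 × (1 − 0.03899) = 115.3 h.
- Censored at 0: 120 h. Gap 4.7 h.
- Censored late: (0.5 − 0.02667)/(1 − 0.02667) = 0.4863, and 120 × 1.0401 = 124.8 h. Gap 9.5 h.

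| M | k | Event at 0 | Censored at 0 (gap) | Censored late (gap) |
|---|---|---|---|---|
| 68 h | 1 | 66.7 | 68 (1.3) | 69.3 (2.7) |
| 68 h | 2 | 65.3 | 68 (2.7) | 70.7 (5.4) |
| 120 h | 1 | 117.7 | 120 (2.3) | 122.4 (4.7) |
| 120 h | 2 | 115.3 | 120 (4.7) | 124.8 (9.5) |

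Against 34 h, the gaps run from 1.3/34 = 4% to 9.5/34 = 28%.

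**The case against.** The strongest reply is that Appendix 7 is legacy text. It calls the endpoint primary, describes a formal weighted test and bootstraps the median difference, whereas the SAP makes time to resolution secondary, tests nothing formally and replaces the bootstrap. The main text refers to it for censoring and interpolation, not for zero times, and Section 2.2.2.1 has its own zero rule. This stands as far as it goes: one cannot say that the rule certainly governs NV20234. It does not remove the conflict. Sections 4.4.2.1 and 4.9 send the programmer to Appendix 7, nothing says which text prevails, and if the rule belongs only to the historical data the comparison mixes two event definitions.

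On (b), the children's zero sentence is probably a slip for a baseline above 1. The adult bullet has that wording, and the individual-symptom bullet, which covers children, gives the same pair of rules. That stands, but correcting it still leaves missing in Section 2.2.2.1 against event at zero in Appendix 7. On (c), the zero sentence can be read as the boundary case in which baseline is the only febrile reading. That is probably what was meant, but the sentence does not say so. The SAP itself warns that interpretation of this endpoint is limited for electronic-diary patients.

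A reader might infer more than the documents support:
- That the rule biases results towards oseltamivir. The direction depends on which side carries the zeros, which the SAP does not show.
- That the shift is large. A 10% share of such patients would lower an exponential median by about 15%, but nothing in the SAP supports that share.
- That censoring at time 0 is already the SAP's alternative. Section 4.4.2.1 says last contact or withdrawal, so the 4.7 h gap is measured against a rule the SAP does not state.

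**Conclusion.** Wrong as written. The three conflicts follow from the wording and need no outside data. Their effect on results is unknown and probably small: (a) needs every non-missing baseline score above 1 and no later diary; (b) affects only all-symptom resolution in children under 13; (c) matters only if fever returns after an afebrile first reading. These are secondary endpoints reported with confidence intervals and no formal test. Neither co-primary endpoint, safety or resistance, is touched.

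The hours for (a) are illustrations that rest on an exponential shape, an assumed median and one or two affected patients in an arm of 75. The late-censoring gap applies to patients who stay in contact without a diary; for an early withdrawal the gap lies nearer the time-0 figure. Most at stake is the comparison with historical placebo, because there the two sides may have been derived under different rules.

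**What to change.** State that Sections 2.2.2.1 and 4.4.2.1 prevail over Appendix 7 for zero times and censoring in NV20234. Then:

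- **(a)** Delete the rule that makes absent later recordings an event at zero, and treat these patients as censored. Give one explicit censoring time in Section 4.4.2.1 for patients with no post-baseline diary. If the last symptom assessment is chosen, say that this amends the present wording on last contact or withdrawal. Do not enter their time as an observed zero in the Hodges-Lehmann estimate: exclude them there, or use a difference method that handles censoring. Apply the same rule to historical patients where the data allow; otherwise add a sensitivity analysis that excludes zero times that cannot be verified.
- **(b)** Correct the children's zero sentence in Section 2.2.2.1 to a baseline above 1, keep children never above 1 as missing, and state that the paediatric zero rule in Appendix 7 does not apply.
- **(c)** Give a fever time of zero only if no later reading is at or above 37.8°C.

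The cost is a few sentences of SAP text and minor recoding before unblinding, with perhaps a few fewer events or evaluable patients. Appendix 4 requests derived times, not diary scores, for the historical datasets, so it cannot be seen from the SAP whether false zeros can be identified there. That is the reason for the fallback sensitivity analysis.
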